### 9.5.2. Withdrawal Procedures

All subjects who are withdrawn from the study will have a post dosing assessment completed. All subjects who received blinded study treatment, with the exception of those for whom consent is withdrawn, will be followed for all subsequent study assessments per study protocol.

### 9.5.3. Replacement of Discontinued Subjects

The study will require a minimum of nine evaluable subjects per treatment group. If more than three subjects do not complete the minimum required duration of study treatment (see [Section 11.3.2](#)) and have a post dosing assessment, subsequent subjects not meeting the minimum required duration of study treatment and follow-up assessments will be replaced.

## 10. DESCRIPTION OF STUDY PROCEDURES

The Schedule of Assessments for the study is provided in [Appendix A](#).

All neonates enrolled in the study will be placed under Universal Precautions and all study personnel with subject contact are trained in appropriate NICU infection control practices.

### 10.1. Informed Consent

After being provided with a full understanding of the study purpose and procedures, the subject's appropriate legally authorized representative(s) (e.g., one or both parents, legal guardian) as defined by local law and IRB/IEC requirements will provide written informed consent and HIPAA authorization using the current version of the IRB-approved informed consent form and HIPAA authorization forms. Consent from both parents (as opposed to only one) will be obtained, if required by the local IRB in accordance with IRB requirements.

The Principal Investigator (PI) and other site personnel as assigned by the PI will be responsible for obtaining informed consent and HIPAA authorization after the study has been explained to the subject's parents/legal guardian and all questions have been answered. The original signed consent form will be filed in the subject's records in accordance with institutional policy and a copy will be provided to the subject's parents/legal guardian. The consent process will be documented in the subject's source documents and the Informed Consent Log supplied for the study.

Written informed consent must be obtained prior to performing any study related procedures.

If a protocol amendment requires revision to the informed consent form, the revised IRB-approved form must be used to obtain and document re-consent from the subject's parents/legal guardian for all subjects currently enrolled in the study.

For mothers below the age of consent and who are emancipated minors, state and local regulations will determine how informed consent and HIPAA authorization are obtained.

### 10.2. History and Baseline Characteristics

The following history and demographic data will be collected:

- Maternal History and Baseline Characteristics – age, ethnicity, race, ongoing medical conditions, concomitant medications, fertility medications taken for this pregnancy (if

applicable), reproductive history, maternal smoking during pregnancy, alcohol use during pregnancy, and recreational drug use during pregnancy.

- Pregnancy History and Delivery – pregnancy complications (description and dates), multiple gestation, gestational age/gestational week at time of delivery, type of delivery, and medications at delivery or around time of delivery. For cesarean section specify whether elective or emergent; for vaginal deliveries specify whether spontaneous, induced, forceps- or vacuum-assisted.
- Infant History and Baseline Characteristics – sex, race, birth date and time, 1- and 5-minute Apgar Scores, birth weight (g), head circumference (cm), length (cm), cord pH and base deficit (if obtained), birth resuscitation/stabilization support used (supplemental oxygen, PPV, CPAP, intubation, chest compression, epinephrine), pre-enrollment medications (e.g., surfactant, antibiotics), date/time of NICU admission. Birth weight will be characterized in relation to gestational age.

### 10.3. Safety Procedures

#### 10.3.1. Physical Examination

Physical examinations will be performed that will include assessments of the following body systems:

- Head, Eyes, Ears, Nose, Throat (HEENT)
- Cardiovascular
- Respiratory
- Central nervous system
- Abdomen/Gastrointestinal
- Genitourinary
- Musculoskeletal
- Dermatologic/Skin

Physical examination findings will be noted in the subject medical records. The screening and Day 1 physical examinations will be recorded on a CRF for the subject. Subsequent physical examinations performed in the NICU will not be recorded on a CRF but all adverse findings meeting the definition of an AE (see [Section 12.2.1](#)), independent of relationship or severity, will be recorded on the CRF as either adverse events or complications of prematurity.

#### 10.3.2. Vital Signs

Vitals signs will include:

- Temperatures (°C) - axillary or by skin probe
- Heart rate (BPM) - measured by auscultation
- Respiratory rate (breaths/minute) – measured by observation

- Blood pressure (mmHg) – measured by either non-invasive (oscillometric) or invasive (arterial pressure transducers) techniques
- SpO2 (pulse oximetry in %)

Vital signs will be noted in the subject medical records. The screening and Day 1 vital signs will be recorded on a CRF for the subject. If there are multiple measurements obtained as standard of care during these study days, the first assessments obtained after noon will be used for the study. The date and time of when these assessments were obtained will be recorded. Subsequent vital signs performed in the NICU will not be recorded on a CRF, but all adverse findings will be recorded on the CRF as AEs.

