## 11. SCHEDULE OF STUDY PROCEDURES

### 11.1. Screening

Parental/legal guardian informed consent must be obtained prior to performing any study procedures.

The following screening procedures will be performed before the first dose of blinded study treatment:

- History and baseline characteristics, including:

- Maternal history and baseline characteristics
- Pregnancy history and delivery information
- Infant history and baseline characteristics
- Physical Examination
- Vital Signs
- Growth Assessment
- Fecal sample, if produced
- Laboratory Assessments
  - Blood Culture (from NICU admission, only if obtained per NICU standard procedures)
- Record concomitant medications

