#### 11.3.2.1. Week 1: Day 1 (Start of Dosing)

Subjects who pass screening evaluations and are eligible for enrollment will be randomized to study treatment.

Prior to dosing, the following study procedures will be performed:

- Physical Examination
- Vital Signs

- Growth Assessment
- Changes in concomitant medications since the screening assessment
- Fecal sample: all fecal samples produced will be collected daily through Day 4 and then once weekly afterward.

Blinded study treatment will be administered to the neonate and the time of administration recorded. Following the initial dose administration, the neonate will be observed continuously by a member of the study staff over the first 60 minutes following administration of study drug and following procedures will be conducted:

- Vital signs every hour ( $\pm 10$  minutes) for 4 hours, then every 4 hours ( $\pm 30$  minutes) through 24 hours following dose administration
- Physical Examination at 3 hours ( $\pm 1$  hour) following dose administration

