Post Dosing 6 Month ^d	181 to 195 days	181 <= (assessment date – expected last dose date+1) <= 195 days
Post Dosing 18 Month/End ^d	Not specified	520 <= (assessment date – expected last dose date+1) <= 576 days
Withdrawal Prior to Post Dosing 6 Month ^d	Not specified	assessment date >= date of withdrawal and (assessment date – expected last dose date+1) <= 181 days
Withdrawal between Post Dosing 6 and 18 Month ^d	Not specified	assessment date >= date of withdrawal and 196 days < (assessment date – expected last dose date+1) < 520 days

- a- Windows for vital sign measurements and physical examinations.
- b- Window for fecal sample.
- c- Window for IVH measurement.
- d- Windows for growth assessment (note that Post Dosing 18 Month data will only be presented in listings).
- e- Windows for Post Dosing may be adjusted to account for patients that terminated dosing early. For example, if a subject early terminates dosing at Week 10 but was expected to complete dosing at Week 11, then the Post Dosing window will be adjusted to reflect planned time point after expected dosing completion.

If a subject has more than 1 assessment occurring in the same visit window, the data from the visit closest to the scheduled study day will be used for summaries. If two assessments have the same distance from the scheduled study day, the assessment after the scheduled study day will be used for the analyses.

If multiple assessments occur as Baseline (screening or Day 1 prior to dosing), then the last assessment before the first study dose will be used for the analyses.

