8.7.4 Other Observations Related to Safety

Growth assessments during the dosing period and post dosing period will be summarized as AGA, SGA/Head-Spared, SGA/Symmetric, LGA at the following time points: Pre-dose, Week 1 (Days 5-7), Week 2, 4, 6, 8, 10, and Post Dosing 1 Week, Post Dosing 1, 3 6 Month, and Early Withdrawal Prior to post dosing 6 Months. Four classifications (AGA, SGA/Head-Spared, SGA/Symmetric, and LGA) according to the growth chart for males and females will be summarized and displayed. Classifications will be based on weight and head growth measurements¹³ specified in Appendix D of the protocol and the WHO standard growth charts https://www.cdc.gov/growthcharts/who_charts.htm.

Information on feeding method (bottle, breast, and tube) and content of feedings (formula or breast milk), abdominal evaluation, etc will be summarized by number and percent of subjects.

Physical examination will be summarized by the number and percent of subjects with abnormal findings at the following time points: Pre-dose, and 3 hours Post Dosing.

Vital signs (BP, HR, RR, and Temperature) will be summarized as descriptive statistics (N, mean, SD, median, 25th and 75th quartiles, minimum, and maximum) and change from baseline at the following time points: Pre-dose, 1 hour, 2, 3, 4, 8, 12, 16, 20 and 24 hours post dosing.

The number and percentage of subjects with presence of STP206 organisms in fecal samples will be summarized, and the quantity (CFU) of the STP206 organisms detected from fecal shedding will be further summarized as descriptive statistics (N, mean, SD, median, 25th and 75th quartiles, maximum, and minimum) at the following time points: Pre-dose, Week 1 Days 1- 4), Week 1 (Days 5-7), Week 2, 3, 4, 5, 6, 7, 8, 9, 10, 11, End of Dosing or Hospital Discharge, whichever occurs first.

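### The after-noon rule for screening and Day 1 vital signs follows the clock, not the dose, and is not reconciled with the pre-dose reading that the SAP needs as baseline

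*Protocol*

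**What the plan says.** Protocol 10.3.2 has the screening and Day 1 vital signs entered on the CRF. It then adds a rule for choosing among several routine readings taken on those days: "the first assessments obtained after noon will be used for the study". It also states: "The date and time of when these assessments were obtained will be recorded". Nothing in that section relates the rule to the time of the first dose.

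Protocol 11.3.2.1 sets out Day 1 around the dose. Under "Prior to dosing, the following study procedures will be performed" it lists vital signs. After the dose it asks for "Vital signs every hour" for 4 hours, then 4-hourly readings through 24 hours. Protocol 11.1 lists vital signs among the items for which "screening procedures will be performed before the first dose of blinded study treatment".

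SAP 6.2.2 says that if there are several baseline readings (screening, or Day 1 before dosing), "then the last assessment before the first study dose will be used for the analyses". SAP 8.7.4 summarises vital signs descriptively with "change from baseline at the following time points: Pre-dose, 1 hour, 2, 3, 4, 8, 12, 16, 20 and 24 hours post dosing".

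The Baseline row of SAP Table 4 is inconsistent within itself. Its protocol-window column includes Day 1 before dosing. Its analysis-window column requires an assessment date strictly earlier than the date of first dose.

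**The concern.** Study day 1 is the calendar date of the first dose (SAP 6.2.1), so it contains readings from both sides of the dose. A rule that picks a reading by the clock cannot tell the two apart. The SAP needs the last reading before the dose, but an analysis rule can choose only among values that were entered. If site staff use the after-noon rule to decide which Day 1 reading to enter, the one that the SAP wants may stay in the medical record.

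The 24 hours after the first dose are the only period for which SAP 8.7.4 specifies a vital-sign change summary, and change in clinical parameters from baseline is part of the primary endpoint (Protocol 6.3.1). Cells are small. Each cohort has 12 infants randomised 2:1, so 8 active and 4 control. One missing baseline removes 1/8 = 12.5% of an active cell or 1/4 = 25% of a cohort's control cell from the change analysis.

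**Working it through.** The plan gives no figure to reproduce. The check lays the after-noon rule over the Day 1 schedule and compares the result with the SAP baseline.

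**Inputs.** The after-noon rule and the recording of times come from Protocol 10.3.2. Scheduled post-dose readings at +1, +2, +3 and +4 h (±10 minutes), then every 4 h to +24 h, come from Protocol 11.3.2.1. The baseline rule comes from SAP 6.2.2. First-dose clock times are assumptions, because the documents give none.

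**General result.** Let D be the dose time and R the first Day 1 reading after noon, so R > 12:00. If D is before 12:00, then R > 12:00 > D, and the selected reading is post-dose whatever the reading schedule.

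**Examples under a literal reading:**

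| Assumed dose | Reading the rule selects on Day 1 | Relation to dose |
|---|---|---|
| 07:00 | 15:00 (scheduled readings at 08, 09, 10, 11 and 15:00) | +8 h |
| 09:00 | 13:00, or the 12:00 reading if taken just after noon | +4 h, or +3 h |
| 11:00 | 13:00, or the 12:00 reading if taken just after noon | +2 h, or +1 h |
| 15:00 | first routine reading after 12:00 | up to 15 − 12 = 3 h before |
| 16:00 | first routine reading after 12:00 | up to 16 − 12 = 4 h before |

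In the three morning rows, a routine reading between noon and the scheduled one would be selected instead, and it too would be post-dose. In the two afternoon rows the selected reading can be pre-dose, but it is the first after noon, not necessarily the last before the dose.

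**What the SAP then does.** It admits only readings before the first dose, and the recorded times allow this to be enforced. In the morning rows the post-dose reading is therefore rejected as baseline. What is left depends on what else is on the CRF:

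1. The scheduled Day 1 pre-dose set was also entered: the baseline is correct and nothing is lost.
2. It was not entered, but a pre-dose screening set was: the baseline is the screening value. Dosing starts within 96 hours of birth (Protocol 10.8.1), so that value is less than 96 hours old, though in a newborn this can still be days.
3. It was not entered, screening fell on the dosing date, and the after-noon rule was applied to screening as well: no pre-dose value is on the CRF. This also departs from Protocol 11.1, which puts screening before the first dose.

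**SAP Table 4.** Read literally, a date strictly before the first-dose date excludes even a correctly recorded Day 1 pre-dose reading, because both carry the same date. That conflicts with the protocol-window column of the same row and with the text below the table. Programmed as written, it would turn case 1 into case 2, or leave no baseline when screening and first dose share a date.

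**The case against.** The strongest reply is about scope. The after-noon rule is worded for multiple standard-of-care readings. The Day 1 pre-dose and timed post-dose readings are protocol procedures. If the rule reduced Day 1 to a single after-noon value, the scheduled post-dose points in SAP 8.7.4 could not be filled either. The coherent reading is that the rule chooses among routine readings and leaves scheduled ones alone. This is a reasonable interpretation, but Protocol 10.3.2 does not state it. The rule covers Day 1 explicitly, and in a NICU a routine reading can readily serve as the pre-dose reading.

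The second reply is that the SAP already protects the baseline. This stands. A reader might infer that a +2 h or +3 h reading becomes the baseline, that the change at that time point is then zero by construction, and that an acute reaction is subtracted out. The documents do not support this: it would require breaching the SAP's before-dose rule although the recorded times allow it to be enforced.

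A reader might also infer that every infant first dosed before noon is affected. That does not follow either. It assumes that each site applies the rule to scheduled readings and omits the pre-dose set.

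Third, comparisons are exploratory, and detection of acute reactions does not rest on the change score. Infants are observed continuously for 60 minutes and examined at about 3 hours, and adverse events are assessed from the first dose. This limits the consequence but does not remove the conflict.

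**Conclusion.** The conflict is real: a clock-based rule in Protocol 10.3.2 is not reconciled with the dose-based reading in Protocol 11.3.2.1 or with the SAP baseline. Applied to Day 1 as written, it selects a post-dose reading after every morning dose and may select an earlier reading than the SAP wants after an afternoon dose.

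The consequence is a possible older or missing baseline for the only vital-sign change summary that the SAP specifies. It is not a demonstrated bias towards zero. For the Day 1 value to be lost, a site must apply the rule to the reading it enters and must not also enter the scheduled pre-dose set. For the baseline to be missing altogether, no usable screening reading may be on the CRF either. The Table 4 window, if programmed literally, has a similar effect without any site error.

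The number of infants affected cannot be determined from the documents, because they give no dosing clock times and no CRF completion instructions. Confidence is high for the conflict and low for the size of its effect.

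**What to change.** In Protocol 10.3.2 and the CRF instructions, state that the after-noon rule does not apply to the Day 1 pre-dose value or to any reading at or after the first dose. Record the last complete set of vital signs before the first dose, with date and time, as the Day 1 pre-dose value. Record post-dose values at the scheduled hours.

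Add an edit check that compares each reading's date and time with that of the first dose and flags any pre-dose value timed at or after it. Where data already exist, retrieve missing pre-dose sets from the medical record, where Protocol 10.3.2 says vital signs are noted.

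In SAP Table 4, redefine the baseline window by date and time rather than date alone, so that a same-day pre-dose reading qualifies and the row agrees with the text below it.

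The cost is a short clarification in each document, one edit check and some chart retrieval. No procedure is added and clinical care does not change.

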### 10.3.3. Growth Assessments

The following assessments of growth will be collected:

- Head circumference (cm) using standard measuring tape
- Body length (cm) using standard measuring tape
- Body weight (g) using digital scale

### 10.3.4. Imaging Examination

Cranial ultrasonography will be performed to ascertain presence/absence of intraventricular hemorrhage (IVH). If IVH is noted, the grade of the IVH will be recorded.

### 10.3.5. Adverse Event Assessment

AEs occurring in neonates will be determined based upon physical findings, functional findings, laboratory findings, and routine observation of the neonate. AEs will be assessed from the time of initial administration of blinded study treatment through 6 months following completion of dosing and be recorded regardless of severity or relationship to blinded study treatment. Ongoing AEs will be followed by standard NICU practice until resolution or stabilization. For each AE, the following information will be recorded:

- Onset date and time
- Resolution date and time
- Severity/intensity (see [Section 12.2.5](#))
- Relationship to study drug (see [Section 12.2.4](#))
- Serious or non-serious (see [Section 12.2.3](#))
- Actions taken to manage/treat the event
- Outcome of the event - resolved, resolved with sequelae, ongoing, death

Complications of prematurity (see [Section 10.5.2](#)) will be recorded separately and not recorded as AEs.

---

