#### **6.3.2. Secondary Endpoints**

The secondary endpoints of the study are:

- The incidence and the severity of AEs and SAEs in STP206-treated subjects compared to control subjects from baseline through six months after the last dose of blinded study treatment
- The incidence of clinical events (NEC, sepsis/bacteremia, feeding intolerance, death, morbidity/complications of prematurity) in STP206-treated subjects compared to control subjects from baseline through hospital discharge
- The assessment of the fecal shedding of STP206 organisms in STP206-treated subjects compared to its baseline and to control subjects through the last dose of blinded study treatment

- The assessment of the changes in routine clinical parameters in STP206-treated subjects compared to control subjects at baseline through the last dose of blinded study treatment
- The assessment of the progression of standard neonatal growth parameters in STP206-treated subjects compared to control subjects through the 6-month postdosing visit.

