## 7.2. Study Treatments

### 7.2.1. Rationale for Dose Selection and Choice of Control Groups

The STP206 doses and treatment duration selected for this study are based upon studies [REDACTED] evaluating [REDACTED]

[REDACTED] The doses planned for this study (total of  $1.1 \times 10^9$  CFU for low dose and  $9.9 \times 10^9$  CFU for high dose) bracket the average dose administered in these studies.

[REDACTED]

[REDACTED]	[REDACTED]	[REDACTED]	[REDACTED]	[REDACTED]
[REDACTED]	[REDACTED]	[REDACTED]	[REDACTED]	[REDACTED]
[REDACTED]	[REDACTED]	[REDACTED]	[REDACTED]	[REDACTED]
[REDACTED]	[REDACTED]	[REDACTED]	[REDACTED]	[REDACTED]
[REDACTED]	[REDACTED]	[REDACTED]	[REDACTED]	[REDACTED]
[REDACTED]	[REDACTED]	[REDACTED]	[REDACTED]	[REDACTED]
[REDACTED]	[REDACTED]	[REDACTED]	[REDACTED]	[REDACTED]
[REDACTED]	[REDACTED]	[REDACTED]	[REDACTED]	[REDACTED]
[REDACTED]	[REDACTED]	[REDACTED]	[REDACTED]	[REDACTED]
[REDACTED]	[REDACTED]	[REDACTED]	[REDACTED]	[REDACTED]

[REDACTED]

[REDACTED]

The dosing duration planned for this study (through 34 weeks of post-conceptual age or hospital discharge, whichever comes first) is consistent with the dosing durations employed in these studies. The dosing duration is also supported by the knowledge that neonates will be at minimal risk of NEC and will be discharged at a post-conceptual age of 34 weeks.

The control group (standard of care plus STP206 reconstitution vehicle) will provide a comparison of incidence of clinical events and study endpoints in a blinded fashion and minimize bias.

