## **11.2. Assessment Schedule for Complications of Prematurity**

### **11.2.1. Necrotizing Enterocolitis (NEC)**

Assessments of signs and symptoms of NEC will be performed daily while the neonate is hospitalized. If NEC is suspected, abdominal X-rays will be performed (see [Appendix B](#)).

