#### *11.3.3.4. 6 Months/End of Study*

The following procedures will be performed between 181 and 195 days following completion of dosing:

- Physical Examination
- Vital Signs
- Growth Assessment
- Assessment of AEs
- Assessment of concomitant medication changes

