## 12. ADVERSE EVENTS

### 12.1. Assessment Period

AEs will be assessed from the time the subject receives their initial dose of study medication through 6 months following the last dose of study drug. All AEs reported during this period, regardless of severity relationship to blinded study treatment, will be recorded.

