### 12.3.1. Reporting Complications of Prematurity

Complications of prematurity will not be classified as AEs, but as study outcomes.

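### Apart from sepsis and bacteremia, a complication of prematurity first diagnosed after hospital discharge cannot be an AE and falls outside the protocol's clinical-event endpoint; the SAP's window differs

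*Protocol*

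**What the plan says.** **AE exclusion.** Protocol 10.3.5 says that complications of prematurity "will be recorded separately and not recorded as AEs". Protocol 12.3.1 repeats it: "Complications of prematurity will not be classified as AEs, but as study outcomes". Neither sentence has an end date. Section 10.5.2 lists the events: NEC, ROP, BPD, IVH, spontaneous gastrointestinal perforation, treated PDA, late onset sepsis and late onset Candida sepsis.

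**Where they are counted instead.** The secondary endpoint in Protocol 6.3.2 covers NEC, sepsis/bacteremia, feeding intolerance, death and complications of prematurity "in STP206-treated subjects compared to control subjects from baseline through hospital discharge".

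**Collection.** Protocol 11.2.1: "Assessments of signs and symptoms of NEC will be performed daily while the neonate is hospitalized". The post-dosing visits (Protocol 11.3.3.1 to 11.3.3.4, the post-dosing schedule in Appendix A, and SAP Table 2) list physical examination, vital signs, growth, AEs and concomitant medication. None lists complications of prematurity.

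**Safety windows.** The primary endpoint (Protocol 6.3.1) covers AEs and SAEs through 30 days after the last dose. AE assessment continues "through 6 months following the last dose of study drug" (Protocol 12.1).

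**SAP.** Section 8.6.2.1 lists NEC, sepsis/bacteremia, feeding intolerance, ROP, IVH, BPD, perforation and treated PDA with no discharge limit; only mortality is confined to the inpatient stay. Section 8 allows summary tables to include data up to the Month 6 post-dose visit.

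**The concern.** Taking serious expected events out of AE reporting is reasonable if another channel counts them for as long as AEs are counted. Here the protocol's other channel closes at discharge, while AE collection runs to 6 months after the last dose. An infant readmitted with NEC, or found to have ROP after going home, has an event that may not be entered as an AE. It cannot be an SAE either, because Protocol 12.2.3 defines an SAE as a kind of AE. It is also outside the protocol's clinical-event endpoint.

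This bears on the primary endpoint and on dose escalation. Under Protocol 7.7 the DSMC sees the previous group's 30-day post-dosing data before deciding on higher doses and lower birth weights, and its packages contain primary and secondary endpoint data. A post-discharge NEC case within those 30 days belongs to neither endpoint as written. With 12 infants per study group (Protocol 7.1), one missing case could change how a group is read.

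**Working it through.** **1. Which events are affected.** Each 10.5.2 event, if first diagnosed after discharge:

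- *NEC, ROP, spontaneous perforation, treated PDA:* barred as AEs (10.3.5, 12.3.1), outside the 6.3.2 endpoint, and not listed at any post-dosing visit. Affected.
- *Late onset sepsis, including Candida:* Protocol 10.3.5.1 makes any sepsis during the study an SAE, and 12.2.3 does the same for confirmed bacteremia. Not lost, although these rules contradict the blanket exclusion.
- *BPD:* Appendix B sets the assessment at 36 weeks or discharge, whichever is first. A later first diagnosis is unlikely.
- *IVH:* ultrasound is at 5 to 7 days of age, and at 28 days only if clinically indicated and the infant is still in hospital (10.5.2.4). A later first diagnosis is unlikely.

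Protocol 12.2.1 also says that worsening of a condition under efficacy evaluation is not an AE. That could be read as a second bar for NEC.

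**2. The plan's own figure.** Inputs: dosing of 14 to 77 days (Protocol Table 2) and a final visit "between 181 and 195 days following completion of dosing" (Protocol 11.3.3.4).

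- Shortest participation: 14 + 181 = 195 days; 195 / 7 = 27.9 weeks.
- Longest: 77 + 195 = 272 days; 272 / 7 = 38.9 weeks.

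These round to the stated 28 to 39 weeks (Protocol 7.4.1), so the windows are being read as the protocol intends.

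**3. Length of the uncovered time.** Let k be the number of weeks from last dose to discharge. The documents do not give k, so these values are assumptions. k = 0 corresponds to Protocol 7.2.1, which expects discharge at 34 weeks, also the planned end of dosing.

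- Uncovered days of the 30-day post-dose primary window = max(0, 30 − 7k).
- Uncovered days of follow-up = 181 − 7k to 195 − 7k.
- Share of participation = uncovered follow-up days / (dosing days + follow-up days).

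| k (weeks) | Of 30 primary-window days | Of 181 to 195 follow-up days | Share, 2-week dosing | Share, 11-week dosing |
|---|---|---|---|---|
| 0 | 30 | 181 to 195 | 93% | 70 to 72% |
| 2 | 16 | 167 to 181 | 86 to 87% | 65 to 67% |
| 4 | 2 | 153 to 167 | 78 to 80% | 59 to 61% |
| 8 | 0 (30 − 56 < 0) | 125 to 139 | 64 to 67% | 48 to 51% |

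Even at 8 weeks, 125 / 181 = 69% of the follow-up is uncovered.

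**4. Protocol against SAP.** The protocol endpoint stops at discharge. SAP 8.6.2.1 gives no stop, and SAP section 8 implies Month 6. SAP 5.2 declares only one change from the protocol's planned analyses, the ITT definition. The SAP therefore neither adopts the protocol's window nor announces a different one.

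**The case against.** A reader might infer that these events are counted nowhere and cannot be recorded at all. The documents do not support that:

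- The discharge limit belongs to an endpoint, not to CRF recording. Sections 10.3.5 and 12.3.1 say that complications are recorded separately, without an end date, and SAP 8.6.2.1 would count a late case that reached the database. This stands. But no post-dosing visit is set up to collect such a case, and the SAP's silence is weak evidence of an intended longer window.
- Sepsis and bacteremia have their own SAE rules. This stands, and they are excluded from the point.
- NEC leading to surgery or death goes to the FDA as blinded desk copies, with no discharge limit (Protocol 12.4.1). This is true, but it is a sponsor submission rule, not an analysis count.

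A reader might also infer that all 30 post-dose days of the primary window are lost. That rests on one sentence in Protocol 7.2.1: "neonates will be at minimal risk of NEC and will be discharged at a post-conceptual age of 34 weeks". Other sections plan for infants still in hospital after dosing: BPD is defined at 36 weeks, and post-dosing stool samples continue until discharge (10.4). The same sentence also calls NEC risk minimal by then, so few NEC cases may be involved. Both limits stand. The sentence does not address ROP, perforation or PDA.

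Finally, recording only late cases as AEs would split one outcome across two systems. That is a fair objection to changing the AE rule alone; the fix answers it by tabulating both windows together.

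**Conclusion.** The point holds for NEC, ROP, spontaneous perforation and treated PDA first diagnosed after discharge. A site that follows the protocol exactly can leave such a case out of the 30-day and 6-month safety results and out of the DSMC's 30-day post-dosing data. It does not hold for sepsis or bacteremia, and it matters little for BPD and IVH.

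The uncovered part of the 30-day primary window is 0 to 30 days: 30 if discharge coincides with the last dose, about 2 at an assumed 4 weeks, and none at 8 weeks. Most of the 6-month follow-up, about 125 to 195 days, is uncovered in every case considered. These are lengths of time, not numbers of lost events; the documents give no rate for post-discharge events. The study is descriptive with exploratory comparisons only, so no power or error rate is affected. What changes is which events the safety analysis contains. The body of the dosing-period schedule table is not in the text reviewed, and nothing is inferred from it.

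**What to change.** **Protocol 10.3.5 and 12.3.1.** Limit the AE exclusion to the initial hospital stay. Suggested text: *After discharge from the initial hospital stay, any event listed in Section 10.5.2 that is first diagnosed is recorded as an AE, and as an SAE if a serious criterion is met, through the 6-month visit.* Add a cross-reference in 12.2.1 so that its exclusion is not read as reaching these events. Reconcile the carve-out with the rule in 10.3.5.1 that any sepsis is an SAE.

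**SAP 8.6.2.1.** State the window and show each complication twice: through hospital discharge, matching the protocol endpoint, and through 6 months after the last dose. Early and late cases then appear together whichever form they were recorded on.

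**Cost.** A CRF completion note, a few more AEs, and one extra row block in Tables 14.2.2 to 14.2.4. No visits are added, because the existing follow-up visits already collect AEs.
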